3.13.2 Treatment Duration

For each of the 3 study periods treatment duration will be Last dose date – First dose date + 1.

For each of the 3 study periods (DEP, RWP, and OLE), treatment duration will be summarized using the SAS populations (defined in [Section 3.5](#)), with results also being presented by responder/nonresponder and treatment group within responder/nonresponder subgroups for the RWP and OLE.

Additionally for the DEP, the duration of time (i.e., days) that a participant was on a dose level that the participant discontinued from will be summarized by dose level and overall.

3.13.3 Distribution of SYNB1934v1 iTD in the RWP

The number and percentage of participants at each of the 3 individual dose levels (3×10^{11} , 6×10^{11} , 1×10^{12}) will be summarized for the RWP using the FAS population (defined in [Section 3.5](#)), with results also being presented by responder/nonresponder and treatment group within responder/nonresponder subgroups.

3.14 Efficacy Analysis

3.14.1 Part 1: DEP

3.14.1.1 Weekly DEP Substudy and Missing Data

Unless otherwise explicitly specified, the additional weekly blood Phe data collected in the subgroup of participants in the DEP Weekly Substudy (see [Section 2.3.2](#)) will not be considered when imputing missing blood Phe data in the DEP efficacy analyses.

3.14.1.2 Primary Efficacy Endpoint Analysis

The DEP primary efficacy endpoint is the percent change from DEP baseline in blood Phe level at the last measurement of the iTD of SYNB1934v1. The last measurement is the participant's last Week 3 blood Phe level at the iTD of SYNB1934v1.

The mean percent change from baseline at the participant's iTD will be tested by an MMRM analysis. The MMRM model will have DEP baseline blood Phe level as a fixed effect. The dependent variable is

the percent change from baseline in blood Phe level at the last measurement of the iTD of SYNB1934v1 (i.e., with duplicate blood Phe assessments being made at the last measurement).

Least-squares means for the percent change from baseline, along with the corresponding [REDACTED] confidence intervals and p-values testing a percent change from baseline equal to 0, will be calculated. The primary efficacy analysis will test the least-squares means percent change from baseline equal to 0 for the blood Phe level at the participants' last week (Week 3) at his or her established iTD.

At each of the scheduled assessments blood Phe will be drawn in duplicate. The MMRM will incorporate the participant repeated/duplicate measures. For the MMRM analysis, the results of the post-baseline duplicate samples from the Week 3 visit will be included in the statistical model (i.e., without averaging the results within a given visit before inclusion into the MMRM).

The MMRM analysis will be based on the restricted maximum likelihood method assuming an unstructured covariance structure to model the repeated-measures. A Kenward-Roger approximation will be used for the denominator degrees of freedom. If there is a convergence problem due to the unstructured covariance matrix, a variance components covariance structure will be used.

The DEP FAS will be the primary efficacy analysis population (defined in [Section 3.5](#)). As the primary efficacy analysis is considering only participants who reach an iTD (see [Section 2.5.1](#)) missing data for the DEP Week 3 blood Phe will generally be limited to those scenarios where the blood Phe sample is not analyzed. In the scenario that a participant is missing both blood Phe values at the DEP Week 3 for their iTD, the following algorithm will be applied:

- If the participant has a corresponding previous non-missing Week 3 blood Phe value at the iTD dose (e.g., the participant escalates to a higher dose then subsequently de-escalates back to a lower dose, which is their iTD) this value will be used.
- Otherwise, the value will remain missing, and an observed-case approach will be used.

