The responder RWP PPS is defined as all responder RWP FAS participants, who had no major protocol deviations that would affect efficacy, had at least 75% treatment compliance, whose dietary Phe remained within 20% of their DEP baseline value, and who did not require systemic antibiotic treatment during DEP or RWP. The responder RWP PPS will be used as a sensitivity analysis for the RWP primary efficacy endpoint. Major protocol deviations will be determined prior to the RWP database lock. Analyses on the responder RWP PPS will be performed according to the randomized treatment group.

Sample Size Considerations:

[REDACTED]. This assumes a dropout rate of 10% in the DEP and approximately 50% of participants are responders. If, during the course of the study, it becomes apparent that the assumptions were not accurate or a dose level is dropped after the interim analysis, the number of participants enrolled into the DEP may be adjusted. The study has over 98% power in testing that the mean percent change from baseline at the last measurement of the iTD in blood Phe level is different from 0. This assumes a mean percent reduction in blood Phe levels of -11%, a standard deviation of 17%, a 10% drop-out rate, and a 2-sided Type I error rate of 0.05. The mean percent reduction and standard deviation in blood Phe values used in the power calculations are based on results from a similar study in participants with PKU.

A sample size of [REDACTED] in the responder RWP [REDACTED] to detect a difference in the mean change in blood Phe level from baseline to Week 4 between the SYNBI934v1 and placebo treatment groups. This assumes a mean treatment group difference in blood Phe of -245  $\mu\text{mol/L}$  between the SYNBI934v1 and placebo groups, a change from baseline standard deviation of 247  $\mu\text{mol/L}$ , 1:1 randomization of SYNBI934v1 and placebo, a 5% drop-out rate in the RWP, and a 2-sided Type I error rate of 0.05. The power was calculated via a t-test. The mean treatment group difference and standard deviation in blood Phe values used in the power calculations are based on results from a similar study in participants with PKU.

Primary Efficacy Analysis:

*DEP (Part 1):* The DEP primary efficacy endpoint is the percent change from DEP baseline in blood Phe level at the last measurement of the iTD of SYNBI934v1. The last measurement is the participant's last Week 3 blood Phe level at the iTD of SYNBI934v1.

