2.5.1 Part 1: Primary and Key Secondary Efficacy Objective Estimands

The estimands corresponding to the Part 1 DEP primary and key secondary objectives and endpoints are described in [Table 4](#) and [Table 5](#), respectively.

Table 4: Estimand for the Part 1 Primary Objective

Objective	To assess the percentage change in blood Phe level
A. Population	The population is the DEP full analysis set (defined in Section 3.5) characterized by the inclusion/exclusion criteria provided in Section 4.2 of the study protocol.
B. Variable	Continuous variable: Percent change from DEP baseline in blood Phe level at the last measurement of the iTD of SYNB1934v1

C. Intercurrent events	
 Participant iTD dose is dropped: As described in Section 2.2, the participant's iTD will be the highest dose tolerated. Additionally, as described in Section 3.17, doses may be dropped at the DEP interim analysis. A treatment-policy strategy approach will be taken in that the participants DEP blood Phe levels on a dropped dose will be included in the DEP primary efficacy analysis. Treatment discontinuation: If a participant permanently discontinues study drug in the DEP, the participant will be asked to have an early termination visit 30 days after last dose of study drug (see Section 5.6 of the study protocol). Treatment discontinuation will follow the treatment-policy approach in that if the participant has reached an iTD (defined as having reached an iTD if they tolerate 3 weeks at a dose, regardless of whether other doses are tolerated) the participants DEP blood Phe levels on a dropped dose will be included in the DEP primary efficacy analysis. A Participant does not reach an iTD: A participant will be defined as having reached an iTD if they tolerate 3 weeks at a dose, regardless of whether other doses are tolerated. A participant who does reach an iTD will not have post-baseline Week 3 blood Phe level assessment. A principal stratum approach will be taken in that the target population of interest is the set of participants who reach an iTD. Antibiotic use: consistent with a treatment-policy strategy, antibiotic use will not be considered (i.e., all observed data will be used regardless of antibiotic use). Prohibited medication use: consistent with a treatment-policy strategy, prohibited medication use will not be considered (i.e., all observed data will be used regardless of prohibited medication use).

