3.14.1.3 Primary Efficacy Sensitivity and Supplementary Analysis

The following sensitivity and supplementary analyses will be performed for the primary efficacy endpoints.

- ***Analysis by iTD:*** The primary efficacy endpoint analysis will be performed on each iTD subgroup.
- ***Imputation of Missing Data:*** Multiple imputation will be used to impute missing blood Phe data during the DEP. The imputation of missing data analysis will assume the data is missing at random (MAR). The methodology for the multiple imputation is provided in [Section 3.18.1](#). As discussed in [Section 3.14.1.1](#), the imputation will not utilize the data from the DEP Weekly substudy. The analysis model will be the same model as the DEP primary efficacy endpoint analysis. The DEP FAS will be the primary efficacy analysis population for this analysis.
- ***Analysis of Covariance:*** The primary efficacy endpoint will be analyzed using an analysis of covariance (ANCOVA) model. The percent change from DEP baseline in blood Phe level at the last

measurement of the iTD of SYNB1934v1 will be the dependent variable is a factor and DEP baseline Phe is a covariate. For this analysis the 2 Phe assessments occurring at the last measurement of the iTD of SYNB1934v1 will be averaged (i.e., if just 1 Phe assessment at this timepoint, that value will be used).

Least-squares means for the percent change from baseline overall dose level, along with the corresponding █ confidence intervals and p-values testing a percent change from baseline equal to 0, will be calculated.

This will be an observed-case analysis using the DEP FAS population, missing data will not be imputed.

- ***Excluding Participants on a Dropped Dose:*** The primary efficacy endpoint analysis will be performed on the DEP FAS using an observed case analysis which excludes participants who were.
- ***Excluding Observations after Treatment Discontinuation, Antibiotic use, or Prohibited Medication:*** The primary efficacy endpoint analysis will be performed on the DEP FAS using an observed case analysis which excludes observations after the following intercurrent events occur in the DEP: Treatment discontinuation, antibiotic use, prohibited medication use.
- ***RWP PPS Analysis:*** The primary efficacy endpoint analysis will be performed using the responder DEP PPS analysis set (defined in [Section 3.5](#)).

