3.14.1.4 Key Secondary Efficacy Endpoints Analysis

The key secondary efficacy endpoint analyses for the DEP are provided below. These analyses will be performed on the DEP FAS.

- ***Change from baseline in blood Phe level at last measurement of the iTD of SYNB1934v1***

The key secondary endpoint, change from baseline in blood Phe level at last measurement of the iTD of SYNB1934v1, will be analyzed using an MMRM analysis similar to the analysis methodology model described for the DEP primary efficacy analysis ([Section 8.4](#)), with the dependent variable being the change in blood Phe level from DEP baseline.

- ***A ≥ 20% reduction from baseline in blood Phe level at any time in the DEP***

The number and proportion of participants meeting this criterion will be summarized along with [REDACTED]. As discussed in [Section 3.14.1.1](#), this analysis will not consider the additional blood Phe data from DEP Weekly substudy. Note this will consider all Week 3 post-baseline blood Phe values occurring in the DEP. This will be an observed-case analysis approach using the DEP FAS such that if a participant is missing the data needed to determine the endpoint, they will be considered as not having met the endpoint.

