3.14.1.5 Key Secondary Sensitivity and Supplementary Analysis

- ***Change from baseline in blood Phe level at last measurement of the iTD of SYNB1934v1***

- ***Analysis by iTD:*** The analysis will be performed on each iTD subgroup.
- ***Imputation of Missing Data:*** Multiple imputation will be used to impute missing blood Phe data during the DEP. The imputation of missing data will assume the data is missing at random (MAR). The methodology for the multiple imputation and analysis is provided in [Section 3.18.1](#). The analysis model will be the same model as the DEP key secondary endpoint analysis. This analysis will be performed on the DEP FAS population.
- ***Analysis of Covariance:*** The change from baseline in blood Phe level at last measurement of the iTD of SYNB1934v1 endpoint will be analyzed using an ANCOVA model. The change from DEP baseline in blood Phe level at the last measurement of the iTD of SYNB1934v1 will be the dependent variable, using the average of the duplicate blood Phe levels (i.e., if one of the values is missing, the non-missing value will be used). The ANCOVA has Treatment as a fixed effect and DEP baseline Phe is a covariate. This will be an observed-case analysis using the DEP FAS population, missing data will not be imputed.

- ***Excluding Observations after Treatment Discontinuation, Antibiotic use, or Prohibited Medication:***

Medication: The key secondary efficacy endpoint analysis will be performed on the DEP FAS using an observed case analysis which excludes observations after the following intercurrent events occur in the DEP: Treatment discontinuation, antibiotic use, prohibited medication use.

- ***RWP PPS Analysis:*** The analysis will be performed using the responder RWP PPS analysis set (defined in [Section 3.5](#)).

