3.20 Changes from the Protocol Planned Analyses

The following are the set of changes from the protocol planned analyses as specified in the study protocol.

These changes will be incorporated into the next study protocol amendment.

- In [Section 2.2.2.1](#), the handling of the scenario when a participant in the DEP de-escalates after RWP randomization is described.
- In [Section 2.5.1](#), the intercurrent events for the estimands were updated. In particular, participants whose dose is dropped during the interim analysis will not be excluded from the analyses.
- In [Section 3.5](#), the DEP FAS was updated to no longer exclude participants whose dose was dropped at the interim analysis.
- In [Section 3.5](#), the DEP FAS was updated to exclude those participants who did not take at least one dose of DEP study medication.
- In [Section 3.5](#), the RWP FAS, responder RWP FAS, and nonresponder RWP FAS were updated to exclude those participants whose dose was dropped at the DEP interim analysis.
- In [Section 3.5](#), the RWP FAS, responder RWP FAS, and nonresponder RWP FAS were updated to exclude those participants who did not take at least one dose of RWP study medication.
- In [Section 3.14.1.2](#), the DEP primary efficacy analysis, iTD was removed as a covariate from the MMRM.
- In [Section 3.14.2.1](#), the RWP primary efficacy analysis, Screening blood Phe was added as a covariate to the MMRM (i.e., as a dichotomous variable: $\leq / > 720 \mu\text{mol/L}$).
- In [Section 3.14.2.6](#), the testing order of the 3 key secondary endpoints in the RWP was not consistent within the study protocol between the synopsis and Section 8.9 of protocol. The correct testing order (i.e., consistent with Section 8.9 of the study protocol) is provided in this SAP.

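### In the single-arm DEP the baseline covariate adds nothing to the estimated mean but narrows its interval: slightly for percent change, materially for absolute change if the effect scales with baseline

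*SAP*

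**What the plan says.** The DEP is one open-label arm, and its primary endpoint is measured at one visit, the last Week 3 draw at the iTD. SAP 3.14.1.2 specifies: "The MMRM model will have DEP baseline blood Phe level as a fixed effect". No other covariate remains, because SAP 3.20 records that "iTD was removed as a covariate from the MMRM". The hypothesis is: "The primary efficacy analysis will test the least-squares means percent change from baseline equal to 0".

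The key secondary in SAP 3.14.1.4 uses a similar model, "with the dependent variable being the change in blood Phe level from DEP baseline". Under SAP 3.14.1.6 it is formally tested once the primary is significant.

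The sensitivity analyses keep the covariate. In the ANCOVA of SAP 3.14.1.3, "DEP baseline Phe is a covariate". For absolute change, SAP 3.14.1.5 has: "The ANCOVA has Treatment as a fixed effect and DEP baseline Phe is a covariate" (treatment has only one level here). The multiple-imputation and by-iTD analyses reuse the main models.

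On the target, SAP Table 4 says: "The population is the DEP full analysis set (defined in Section 3.5) characterized by the inclusion/exclusion criteria". For power, the protocol synopsis (Sample Size Considerations) says: "This assumes a mean percent reduction in blood Phe levels of -11%, a standard deviation of 17" (in per cent), with 10% drop-out, a two-sided 0.05 level and power over 98%.

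**The concern.** In a randomized comparison, a baseline covariate corrects chance imbalance between arms and so earns its smaller standard error. The DEP has no second arm and nothing to correct. At the sample's mean baseline the fitted mean is the sample mean, with or without the covariate, but the model's standard error treats that mean baseline as a known constant. Another sample from the same eligible population would have a different mean baseline. If change depends on baseline, that variation is real sampling error in the mean change, and the model leaves it out. The Kenward-Roger adjustment does not restore it, because it also conditions on the covariates.

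At stake is whether the reported DEP intervals, and the multiplicity-controlled test of absolute change, meet their stated level. Every DEP sensitivity interval that keeps the covariate shares the problem, so agreement among them would not reveal it. General descriptive means and SDs are planned, but no unadjusted one-sample interval or test is.

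**Working it through.** **Stated power first.** With a mean of -11, an SD of 17 and a two-sided 0.05 level, the exact one-sample t-test reaches 98.1% power at 41 evaluable participants, which is 41/0.9, or 46 enrolled. The DEP sample size is redacted, so the statement of over 98% cannot be reproduced. It is consistent with any enrolment of about 46 or more. It uses the SD of percent change and mentions no gain from a covariate.

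**Algebra (averaged duplicates, n participants).** Y is the outcome, B the baseline, b the fitted slope and R² their squared correlation.

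- LS mean at the mean baseline = mean of Y, for any b.
- Unadjusted SE = SD/√n.
- Model SE = SD·√[(1-R²)(n-1)/(n-2)]/√n.
- Omitted term = b²·Var(B)/n = R²·SD²/n. Adding it to (1-R²)·SD²/n restores SD²/n.

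REML fits with an unstructured 2×2 covariance for the duplicates, on data built with strong baseline dependence, agree. Adding baseline moved the estimate by about 2 µmol/L at most (estimates -207 to -309), while the SE fell to 0.55-0.76 of its unadjusted value. The small shifts come from the estimated weighting of the duplicates and from missing duplicates.

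**Planned SD, n = 41.** Unadjusted SE = 17/√41 = 2.65 points; 95% half-width = 2.021 × 2.65 = 5.37. Adjusted half-widths are 5.44 at R² = 0, 5.16 at 0.10, 4.86 at 0.20 and 4.55 at 0.30. Below an R² of about 0.025 the lost degree of freedom makes the adjusted interval slightly wider.

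**Coverage against R² (assumed n = 60).** Coverage ≈ P(|t₅₉| < 2.002·√[(1-R²)·59/58]):

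| R² | Model SE / unadjusted SE | Coverage of nominal 95% interval |
|---|---|---|
| 0.05 | 0.983 | 94.6% |
| 0.10 | 0.957 | 94.0% |
| 0.15 | 0.930 | 93.2% |
| 0.20 | 0.902 | 92.4% |
| 0.30 | 0.844 | 90.4% |
| 0.50 | 0.713 | 84.1% |

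**What R² could be.** The documents give no baseline SD, correlation or R², so these are assumptions.

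- *No drug effect, equal variances at both visits.* For absolute change R² = (1-ρ)²/[2(1-ρ)] = (1-ρ)/2. At ρ = 0.9, 0.8 and 0.7, R² is 0.05, 0.10 and 0.15. From the table, the type I error of that test taken alone is 5.4%, 6.0% and 6.8%.
- *Effect proportional to baseline, simulated* (n = 60, between-person CV 35-45%, within-person CV 10-20%). Absolute-change coverage is about 93-94% with no effect (type I error about 6-7%), 90-92% at -11% and 73-82% at -30%. Unadjusted intervals cover about 94-95%.
- *Percent change in the same model.* A within-person CV of about 13% reproduces the planned SD of 17%. The SE is then about 2-3% too small and coverage about 94-95%.
- *Proportional effect with percent-change SD set near 17%* (baseline CV 0.3-0.5, within-person CV 0-0.10, the rest being person-to-person variation in effect). Absolute-change R² is 0.03-0.15 at -11% (coverage 92.2-94.4%) and 0.25-0.50 at -34%, the mean decrease in the earlier phase 2 study cited in Protocol 1.7 (coverage 83-91%). Percent change stays at about 95%.
- *Constant absolute effect.* The order reverses: absolute change covers about 95% and percent change 90-95%.

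**The case against.** The strongest objection is that conditioning on observed baselines is ordinary regression practice, and that Table 4 names the DEP full analysis set as the population. For the narrower target, mean change at this sample's mean baseline, the interval is valid. That stands as a description of what the model estimates. But Table 4 goes on to characterize the population by the eligibility criteria, which do not fix the mean baseline, and the SAP states no conditional target.

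Several limits also stand. The primary is barely affected at the planned SD. The upper end of the within-person range (20%) implies a percent-change SD of about 26% at -11%, which does not fit the planned 17%. The ranking of the two endpoints depends on the effect model. Absolute change is tested only after the primary succeeds, so with no effect on either endpoint an error must first pass a nearly unaffected test. Low coverage at large effects is a fault in precision; rejection of zero is not in doubt there.

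A reader might also infer three stronger points that the documents do not support:

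- *The power calculation is wrong.* Planning on an SD without a stated covariate gain and then fitting a prespecified covariate is not an error, and the stated power is unaffected.
- *A proportional drug effect inflates type I error.* A nonzero effect is not the null. Under no effect, only regression to the mean acts.
- *The DEP result or the main efficacy claim is in doubt.* With power over 98%, the DEP conclusion is unlikely to flip. SAP 2.1 names the randomized RWP comparison as the primary evidence, and it is unaffected.

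**Conclusion.** The concern holds as a fault in the DEP standard errors. The point estimate is the raw mean (exactly so with averaged duplicates), and the covariate only removes a real part of its sampling variance. For the percent-change primary the effect is small at the planned SD. For the tested absolute-change key secondary it is material if the effect scales with baseline, and it grows with the effect. The figures rest on an assumed n and assumed CVs. They are milder if individual percent effects vary, and the order of the endpoints reverses under a constant absolute effect. The correction is worth making because the reported intervals should have their stated coverage, not because the trial's conclusions are at risk.

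**What to change.** For both DEP continuous endpoints (SAP 3.14.1.2 and 3.14.1.4), make the tested analysis an intercept-only MMRM or a one-sample t-test on the averaged duplicates. Keep the baseline-adjusted model only as a sensitivity analysis. If it must remain the tested analysis, add b²·Var(baseline)/n to the variance of the least-squares mean.

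Make the same change in the ANCOVAs and in the imputation and by-iTD analyses that reuse the covariate, and list it in SAP 3.20, since Protocol 8.4.1 also has baseline in the model.

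The cost is edits to a few SAP sections and the matching code, and a modestly wider interval. The estimate is essentially unchanged, and the test then corresponds directly to the power calculation.

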2.3.1 Blood Phenylalanine and Tyrosine

Blood Phe and Tyr samples will be drawn 2.5 to 5 hours after the last meal. Phe and Tyr samples will be drawn in duplicate, using separate tubes from the same venipuncture, and analyzed separately. The time of the last meal will be recorded when taking Phe samples.

Baseline samples for DEP and RWP must be drawn prior to the first dose for those respective periods. During the DEP, blood Phe and Tyr will be measured at Week 3 of each completed dose level. During the OLE, blood Phe and Tyr will be measured quarterly. Blood Phe and Tyr will also be measured at early termination.

For all Tyr summaries the average value will be used, with the individual duplicate values being presented in the listings.

The individual duplicate blood Phe values will be used in some analyses, and the average of the duplicate values used for other analyses and summaries (see [Section 3.3](#)).

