- ***MMRM Analysis by Dose Level:*** The percent change in blood Phe level will be analyzed using an MMRM model. All available Week 3 blood Phe data will be used. The model will have percent change from baseline as the dependent variable. Dose level (as a categorical variable) and baseline blood Phe will be fixed effects. The MMRM analysis will be based on the restricted maximum likelihood method. A Kenward-Roger approximation will be used for the denominator degrees of freedom. The covariance structure for the repeated-measures will be a direct product of unstructured for the multiple Week 3 visits (i.e., a total of 5 possible Week 3 visits, 3 for each dose level and 2 for possible repeats of the 3×10^{11} and 6×10^{11} doses) and compound symmetry for the repeated assessments at a particular visit. As such the covariance structure will use the direct product structure “UN@CS” as defined in SAS PROC Mixed.

This will be an observed-case analysis, this analysis will be performed using the DEP FAS and also using the responder RWP FAS population, missing data will not be imputed.

If the MMRM analysis does not converge, the repeated measures at each blood Phe assessment will be averaged together and the average of the repeated measures will be used to calculate the percent change in blood Phe level, the dependent variable. The model will have percent change from baseline as the dependent variable (i.e., using the averaged value at Week 3 visit). The MMRM model will be the same (i.e., same set of fixed effects) with the exception that the covariance structure for the repeated-measures will be unstructured for the multiple Week 3 visits (i.e., a total of

5 possible Week 3 visits, 3 for each dose level). If this model does not converge a compound symmetry covariance structure will be used.

Additionally, histograms illustrating the DEP Week 3 change and percent change from baseline in blood Phe by treatment group will be produced, overall and by iTD.

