3.14.2.1 Primary Efficacy Endpoint Analysis

The RWP primary efficacy endpoint is the change from RWP baseline to Week 4 in blood Phe level. An MMRM analysis will be used to compare the mean change in blood Phe level between the placebo and SYNB1934v1 dose groups. The MMRM model will have treatment group, Screening Blood Phe (as a dichotomous variable: $\leq / > 720 \mu\text{mol/L}$), RWP baseline blood Phe level, iTD dose level, visit, and visit \times treatment group (interaction effect), visit \times iTD dose level (interaction effect), and visit \times RWP baseline blood Phe level (interaction effect) as fixed effects. The MMRM will also incorporate the participant's repeated measures at visits Weeks 1, 3, and 4, with visit being treated as a categorical variable. Least-squares means for both treatment groups and the SYNB1934v1 treatment group difference from placebo, along with the corresponding [REDACTED] confidence intervals and p-values will be calculated for Weeks 1, 3, and 4. The primary efficacy analysis will compare the least-squares means treatment difference between SYNB1934v1 and placebo in the change from baseline in the blood Phe level at Week 4.

At each of the scheduled assessments, blood Phe will be drawn in duplicate. The MMRM will incorporate these participant repeated measures. For the MMRM analysis, the results of each of the post-baseline duplicate samples from a visit will be included in the statistical model (i.e., without averaging the results within a given visit before inclusion into the MMRM).

The MMRM analysis will be based on the restricted maximum likelihood method. A Kenward-Roger approximation will be used for the denominator degrees of freedom. The covariance structure for the repeated-measures will be a direct product of unstructured (i.e., for the visits) and compound symmetry for the repeated assessments at a particular visit (i.e., the subject-level repeated measures has 2 dimensions, post-baseline Weeks 1, 3, and 4, as well as the 2 assessments at each visit. As such the covariance structure will use the direct product structure "UN@CS" as defined in SAS PROC Mixed).

For the dependent variable, this will be an observed-case analysis using the responder RWP FAS population, missing data will not be imputed.

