3.14.2.2 Primary Efficacy Analysis Model Does Not Converge

If the RWP primary efficacy MMRM analysis does not converge, the repeated measures at each blood Phe assessment will be averaged together and the average of the repeated measures will be used to calculate the change from baseline in blood Phe level, the dependent variable. The model will have change from baseline as the dependent variable. The model will have percent change from baseline as the dependent variable (i.e., using the averaged value at each of the Week 1, 3, and 4 visits). The MMRM model will be the same (i.e., same set of fixed effects as described in [Section 3.14.2.1](#)) with the exception that the covariance structure for the repeated-measures will be unstructured to account for the within-subject Week 1, 3, and 4 assessments. If this model does not converge, a compound symmetry covariance structure will be used.

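### If the DEP primary model does not converge, the stated fallback (read as a diagonal matrix) counts two tubes from one blood draw as independent, and the standard error comes out about 18% to 29% too small

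*SAP*

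**What the plan says.** The DEP primary endpoint is percent change in blood Phe at the last Week 3 visit on the individually titrated dose (iTD). Phe is drawn in duplicate, "using separate tubes from the same venipuncture, and analyzed separately" (SAP 2.3.1). Both values enter the model, "without averaging the results within a given visit before inclusion into the MMRM" (SAP 3.14.1.2). The model has an intercept and DEP baseline Phe, REML estimation, an unstructured covariance for the repeated measures and Kenward-Roger degrees of freedom. The rule for failure to converge is: "If there is a convergence problem due to the unstructured covariance matrix, a variance components covariance structure will be used".

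The SAP treats the same duplicates differently elsewhere:

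- In the DEP by-dose MMRM, on non-convergence, "the repeated measures at each blood Phe assessment will be averaged together" (3.14.1.3). The counterpart for absolute change in 3.14.1.5 has the same rule.
- In the primary model of the randomized withdrawal period (RWP), on non-convergence, "the average of the repeated measures will be used to calculate the change from baseline in blood Phe level" (3.14.2.2).
- The RWP primary model itself uses "compound symmetry for the repeated assessments at a particular visit" (3.14.2.1).

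**The concern.** The DEP primary analysis uses one visit per participant, so the only covariance to model is the 2x2 matrix of the two tubes. If a variance components structure replaces the unstructured matrix and no random participant effect is named, the natural reading in SAS PROC MIXED is a diagonal residual matrix. The tubes are then assumed uncorrelated and n participants supply 2n independent records. Kenward-Roger does not repair this: the assumed covariance is itself wrong, and the denominator degrees of freedom become about 2n - 2 instead of n - 2.

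What is at stake is the DEP primary confidence interval (too narrow) and p-value (too small) whenever the fallback is used. The absolute-change key secondary, which is formally tested, "will be analyzed using an MMRM analysis similar to the analysis methodology model described for the DEP primary efficacy analysis" (3.14.1.4) and so would probably inherit the rule. The same primary analysis is repeated by iTD (3.14.1.3) and in the sapropterin and genotype subgroups (3.14.1.9), some of which may be small.

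**Working it through.** **Inputs.** Two-sided alpha 0.05 (Protocol 8.9). Planning mean -11%, SD 17%, 10% dropout, power over 98% (Protocol synopsis, Sample Size Considerations). The documents give no tube-to-tube correlation rho, so a range of 0.5 to 0.99, conditional on baseline, is assumed. The sample size is redacted.

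**The plan's own figure.** With N redacted, the stated power cannot be reproduced exactly. A one-sample two-sided t-test with mean -11 and SD 17 first exceeds 98% at n = 41 analysed (98.1%), which is 41/0.9 = 45.6, or 46 enrolled. The result below does not depend on n.

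**Standard error.** Take n participants, two tubes each, tube variance s² and correlation rho:

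- true variance of the mean: s²(1 + rho)/(2n)
- variance reported by the diagonal fit: s²/(2n)
- ratio of reported to true SE: 1/sqrt(1 + rho)
- actual two-sided type I error: 2[1 - Φ(1.96/sqrt(1 + rho))]

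| rho (assumed) | SE ratio | SE too small by | Type I error | Coverage of nominal 95% CI |
|---|---|---|---|---|
| 0.5 | 0.816 | 18.4% | 11.0% | 89.0% |
| 0.8 | 0.745 | 25.5% | 14.4% | 85.6% |
| 0.9 | 0.725 | 27.5% | 15.5% | 84.5% |
| 0.99 | 0.709 | 29.1% | 16.5% | 83.5% |

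The limit at rho = 1 is 29.3% and 16.6%.

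**Where in the range.** With a total SD of 17 points, the within-draw SD is 17·sqrt(1 - rho): 12.0 points at rho 0.5, 5.4 at 0.9 and 1.7 at 0.99. Two tubes from one draw, set against the same baseline mean, should lie toward the upper end, though the documents cannot settle this.

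**Simulation under the null.** 20,000 datasets per cell, SD 17, baseline covariate, n = 41 and n = 90 (the latter an assumption). The diagonal fit rejected in 10.9% to 17.4%, with coverage 89.1% to 82.6%. The fit on averaged duplicates rejected in 4.8% to 5.2%. A separate run (4,000 datasets per cell, n = 40, 60 and 150) gave SE ratios of 0.816 to 0.817 at rho 0.5 and 0.700 to 0.707 at rho 0.99.

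**Small subgroups.** At assumed n = 8 and n = 12 with rho 0.99, the diagonal fit rejected in 20.4% and 18.9%, against 5.0% and 4.8% with averaging.

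**Effect on the decision at the planning values.** In 100,000 datasets per cell with a true mean of -11%, the diagonal fit was significant and the averaged fit was not in 0.25% (rho 0.5) to 1.43% (rho 0.99) at n = 41, and in 0 to 0.001% at n = 90.

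**How often the fallback would be needed.** REML fits of the unstructured 2x2 model, 400 per cell at rho 0.5, 0.9 and 0.99 and n = 41 and 90, failed in 0 of 2,400. They used a BFGS optimiser, not PROC MIXED, and t with n - 2 degrees of freedom, not Kenward-Roger. Rejection under the null was 4.8% to 7.3% for the unstructured model and 4.3% to 6.8% for compound symmetry (Monte Carlo SE about 1.1 points). Convergence in small subgroups was not checked.

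**The case against.** The strongest reply is that the trigger is nearly empty. With 0 failures in 2,400, the 95% upper bound on the failure rate is 3/2,400 = 0.125%. Multiplied by the worst excess (16.5 - 5 = 11.5 points), the unconditional rise in type I error is about 0.014 points. This stands for the conditions checked, but it does not carry over directly to PROC MIXED on real data or to small subgroups.

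Second, n = 41 is probably smaller than planned. The RWP assumptions (-245, SD 247 µmol/L, 5% dropout, about 50% responders) need 34 analysed responders for 80% power and 46 for 90%. Dividing by 0.95 and then by 0.5 gives about 72 to 97 DEP completers. RWP power is redacted, so 80% to 90% is itself an assumption. On this view the n = 90 result applies, and the decision almost never changes. That is fair.

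Third, a random participant intercept plus residual is also a variance components model and would be valid. True, but the SAP does not specify one. A contingency rule with one valid and one invalid reading leaves the choice until the data are in hand.

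Fourth, a correct analysis is already planned: in the DEP ANCOVA of 3.14.1.3, "For this analysis the 2 Phe assessments occurring at the last measurement of the iTD of SYNB1934v1 will be averaged". A discrepancy would be visible in the report. This limits the harm but leaves the designated primary result wrong.

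Fifth, inheritance by the key secondary is inference. SAP 3.14.1.4 says only that the model is similar and refers to Section 8.4, and Protocol 8.4.1 states no covariance structure or fallback. This is accepted.

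**Conclusion.** The concern holds. Read as a diagonal structure, the fallback gives a standard error 18% to 29% too small and a type I error of 11.0% to 16.5% at a nominal 5%. This rests on three conditions: that the unstructured model fails to converge, that the diagonal reading is applied, and that rho lies in the assumed range of 0.5 to 0.99. It applies to participants with both tubes and shrinks slightly if some have only one. The unstructured model itself is valid; only the fallback sentence is at fault. The realistic harm is a DEP primary interval that is too narrow. A changed conclusion is unlikely. The RWP, which SAP 2.1 names as the source of the primary evidence of efficacy, is unaffected. The point is worth correcting but does not threaten the trial's main conclusion.

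**What to change.** In SAP 3.14.1.2, replace the fallback with: *on non-convergence, the two Week 3 values are averaged (a single available value is used as it stands) and the model is fitted to one value per participant.* This follows the averaging step of 3.14.2.2. With one record per participant it reduces to the ANCOVA of 3.14.1.3. Specifying compound symmetry for the duplicates would serve equally well and keep both records in the model. If a random participant intercept was intended, the SAP should say so.

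State in 3.14.1.4 that the same fallback applies to the absolute-change key secondary.

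The cost is one SAP sentence and a cross-reference. The planned first-choice analysis does not change. The only downside is a wider, correct interval if the fallback is used.
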